	This will be a single-center, prospective, unblinded, non-randomized study of 120 immunosuppressed patients who are planning to receive a NVX-CoV2024-2025 COVID-19 booster
FDA Regulatory Overview	The protocol uses an investigational product, NVX-CoV2601, and is being conducted under IND NUMBER 29913 that is held by [name].
Study Intervention	NVX-CoV26012023/2024 (monovalent, XBB containing) Novavax COVID-19 vaccine, the Omicron XBB.1.5 vaccine is named BV2601 NVX-CoV2024-2025 booster Novavax COVID-19 vaccine, the Omicron XBB.1.5 vaccine is named BV2601
Total Number of Subjects	2023-2024 season 21 patients were enrolled in this season 2024-2025 season (none will be recruited anymore) (The 2024-2025 season activities will not proceed as originally planned due to the withdrawal of financial support from our sponsor). A total 120 subjects will be enrolled.
Ota-la B	A total of 141 subjects will be enrolled for this study for both seasons.
Study Population	Male and females aged 18 to 85 with IBD and/or who are solid organ transplant recipients.
Statistical Methodology	In analyzing the primary endpoint, a paired t-test will be utilized to test whether, on average, there is a change of at least 15% antibody blood concentration between the first and second

	blood draws. A test statistics and degrees of freedom, including the 95% confidence intervals will be reported. In addition, we will model the post measurement blood draw concentrations (i.e., V2 and V3) as the response variable using an ANOVA (i.e., ANOVA-POST), while adjusting for the initial responses (V1) and other baseline covariates.
Estimated Subject Duration	The duration of the study for each subject is approximately 6 months.
Estimated Enrollment Period & Study Duration	Study enrollment and follow-up will occur over 6 months with the total expected duration of the trial to be 24 months.

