Success Criterion: Descriptive

6.4 Evaluate the disease activity following administration of the booster dose up to 30 days post-vaccination and during the whole post-vaccination follow-up period.

Disease activity will be assessed by monitoring disease activity using the Short Crohn's Activity Index (SCAI)¹⁹ for patients with Crohn's disease or the Simple Clinical Colitis Activity Index (SCCAI) questionnaire for patients with Ulcerative colitis at the baseline visit (V1), V2, and V3 visits. For patients with pouchitis we will use the simplified pouchitis disease activity index (PDAI). The incidence of IBD flares will be evaluated in all patients receiving recombinant boosters. This will be quantified by patients who were in clinical remission who develop a disease flare after receiving a recombinant COVID-19 booster.

Endpoint:

The number and percentage of participants reporting disease flares of IBD.

Success Criterion: Descriptive

6.5 Evaluate for solid organ transplant rejection following administration of booster dose, up to 30 days post-vaccination and during the whole post-vaccination follow-up period.

Participants will be asked if they have been diagnosed with acute rejection after their baseline visit (V1). Episodes of acute rejection will be collected by searching electronic medical records and asking patients at each clinic visit (V2 and V3). Acute rejection will be defined as a notation of a new episode of acute rejection (cellular or antibody-mediated), a steroid bolus and taper in the absence of another indication, or administration of a T or B cell depleting agent or immune globulin.²⁰

This will be quantified by patients who develop acute rejection of their transplant after receiving a recombinant COVID-19 booster.

Endpoint:

The number and percentage of participants reporting acute rejection of their transplant.

Success Criterion: Descriptive

[figure not shown]

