8.2 Exclusion criteria

A patient will not be eligible for inclusion in this study if they meet any of the following criteria.

- Allergy to recombinant COVID-19 vaccine or any component of it
- Patient cannot or will not provide written informed consent.
- Unable to provide appropriate informed consent because of illiteracy or impairment in decision-making capacity.
- Active antibody-mediated or cellular rejection within the past six months
- Recent IBD flare requiring initiation of systemic corticosteroids within the past month
- Previous history of myocarditis or pericarditis ever.
- Patients who are pregnant
- Patients who are lactating
- Patients with an active COVID-19 infection
- Patients with a COVID-19 infection within the past two months

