13.21 Adverse Events of Special Interest

Myocarditis and pericarditis will be adverse events of special interest. All patients will be counseled on the potential risk of myocarditis or pericarditis from COVID-19 vaccination.

- 1) Potential myocarditis and pericarditis events
- a. Participants reporting acute chest pain, shortness of breath, palpitations, or other signs or symptoms of myocarditis or pericarditis within 4 to 6 weeks after vaccination must be referred to a cardiologist for evaluation and management.
- b. Cases of myocarditis and pericarditis will be followed until resolution of symptoms and abnormal test findings.

Myocarditis and pericarditis cases will be defined by based on the Centers for Disease Control and Prevention (CDC) care definition. ²³ (Appendix 5)

- 2) IBD flares will be evaluated based on SCAI, PDAI, and SCCAI based on follow-up at V1, V2, & V3..
- 3) Solid organ transplant rejection will be reviewed based on follow-up at V1, V2, & V3. Episodes of acute rejection will be documented by chart review.

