13.26 Safety Oversight and Stopping Rules

To evaluate whether the vaccine results in SAE, IBD flares, transplant rejection, or myocarditis/pericarditis these will be monitored with the following DSMP. For every 40 patients enrolled in the study, the rate of SAE and IBD flares or episodes of acute rejection will be reviewed. SAE will be reviewed based on follow-up at V1, V2, V3, and vaccine diaries. IBD flares will be evaluated based on SCAI, PDAI, and SCCAI, and episodes of acute rejection will be documented by chart review. Episodes of potential myocarditis or pericarditis will be reviewed after evaluation by a cardiologist and defined based on CDC case definition (appendix 5).A The Principal Investigator (PI) will be responsible for reviewing these data will be reviewed continuously and pause the study if any stopping rules are met. He will have the SMC review the AE and determine if study should be stopped.

The study will be halted if any of the following criteria are met:

- Any serious AE occurs, including death, that is assessed as related to the product and occurring within the entire length of the study.
- Three or more participants experience the same or similar grade 3 or greater AEs, including laboratory abnormalities, that are assessed as related to the product, and occurring within the entire length of the study.
- More than 5 participants have an IBD flare of at least moderate activity (defined by the Short Crohn's Disease Activity Index [sCDAI], Simplified Pouchitis Disease Activity Index [PDAI], or the Simple Clinical Colitis Activity Index [SCCAI]) without a known cause.
- More than 4 participants have allograft rejection that requires treatment without a known cause. ²⁴
- More than 2 participants have an episode of myocarditis or pericarditis.

In the event that study stopping rules are met, enrollment and vaccine administration in the study will be paused while an assessment by the Sponsor-Investigator takes place.

Progress reports and notifications of unanticipated problems, adverse events, protocol deviations, and protocol violations will be reported to the IRB per the posted guidance.

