13.27 Study Monitoring

We will use an internal safety monitoring committee (SMC) comprised of experienced clinical researchers representing a diversity of backgrounds, skills and knowledge. The SMC helps investigators ensure subject safety, research integrity, and compliance with federal regulations and local policies. The SMC also makes recommendations to the PI that could include actions of continuation, modification, suspension, or termination.

The SMC will be able to meet on an adhoc basis to review any number of AE, SAE, or AE of special interest that may have met the stopping rules. They will determine if these events have met the criteria for halting the study. Recruiting will halt until the SMC has determine whether the stopping rules have been met. If the SMC determines the stopping rules have not been met then resumption of enrollment will continue.

Clinical site monitoring is conducted to ensure that the rights and well-being of human subjects are protected, that the reported trial data are accurate, complete, and verifiable, and that the conduct of the trial is in compliance with the currently approved protocol/amendment(s), with GCP, and with applicable regulatory requirements.

- Monitoring for this study will be performed by the University of Wisconsin Madison's Central Monitoring Service.
- On site monitoring will be conducted for this study which will include a site initiation visit, interim monitoring visits, and close out visit as outlined in the clinical monitoring plan.
 Monitoring will include review of regulatory files, investigational product, and up to 20% of subject records and data. Additional records may be reviewed, as needed, to ensure compliance with applicable regulatory requirements.

•	The sponsor-investigato visit.	r will be provided co	ppies of monitoring re	eports within 30 days of

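### The acute-rejection definition requires that there be no other indication only for steroids, so a depleting agent or immune globulin given for any reason meets the descriptive rejection endpoint as written

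*Combined protocol and SAP*

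**What the plan says.** Section 6.5 gives the case definition in one sentence. It opens with a chart-based criterion: "Acute rejection will be defined as a notation of a new episode of acute rejection (cellular or antibody-mediated". It then adds treatment-based criteria: "a steroid bolus and taper in the absence of another indication, or administration of a T or B cell depleting agent or immune globulin". Section 10.4.2 repeats the definition with the condition in the same place.

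The endpoint built on it in section 6.5 is "The number and percentage of participants reporting acute rejection of their transplant", and its success criterion is descriptive. Cases come from asking participants and searching the electronic record. Section 13.21 lists rejection among the events of special interest and says "Episodes of acute rejection will be documented by chart review".

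The stopping rule in section 13.26 uses different words: "More than 4 participants have allograft rejection that requires treatment without a known cause". Section 13.27 describes the safety committee's part: "They will determine if these events have met the criteria for halting the study".

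On size, the synopsis states for 2023-2024 that "21 patients were enrolled in this season", and that nobody further will be recruited. It does not say how many of the 21 are transplant recipients.

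**The concern.** Treatment is a proxy for the event that the endpoint is meant to count, and a proxy works only if treatment given for other reasons is set aside. The plan does this for steroids but not for depleting agents or immune globulin. An abstractor who follows the sentence literally has to count any recipient who received one of those agents, whatever the chart gives as the reason.

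Section 14.1 names transplant rejection as one of two areas to be closely monitored. The study is non-randomized and has no unvaccinated comparator, so a misclassified case is not offset anywhere. It would appear in the report as rejection after vaccination. At stake is what the reported number and percentage mean, because that count is all this endpoint delivers.

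**Working it through.** The documents give no figure for this point, so there is nothing to reproduce. The check is mainly textual, with one calculation to see whether the stopping rule is exposed.

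**1. Parsing the definition (sections 6.5 and 10.4.2).** Each alternative is sufficient on its own.

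| Alternative | Condition attached |
|---|---|
| Charted new episode, cellular or antibody-mediated | It is itself a diagnosis |
| Steroid bolus and taper | No other indication |
| T- or B-cell-depleting agent, or immune globulin | None |

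The third alternative follows a comma and a fresh conjunction, so the condition in the second does not carry forward. The repetition in section 10.4.2 makes a one-off slip of punctuation less likely.

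**2. Looking for a restriction elsewhere.**
- Section 8.2 excludes patients with "Active antibody-mediated or cellular rejection within the past six months". It has no criterion on immune globulin or depleting agents.
- Section 13.21 provides for chart review, with no step that judges why a treatment was given.
- Section 13.27 has the committee decide whether halting criteria are met. It is not asked to adjudicate the endpoint.
- Section 10.1 collects concomitant medications at V1, V2 and V3. No indication field is described.

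None of these limits the third alternative to treatment given for rejection.

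**3. Denominator.** The endpoint is worded as a percentage of participants. The population includes people with IBD and no graft, who cannot have the event. The plan does not say that the percentage is taken among transplant recipients.

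**4. Is the stopping rule exposed?** More than 4 means 5 or more. Let n be the number of transplant recipients and q the chance that a recipient gets one of these agents for a reason other than rejection. Both are assumptions; the documents bound n only by the 21 enrolled. With X binomial(n, q):

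P(X ≥ 1) = 1 − (1 − q)^n, and P(X ≥ 5) = 1 − Σ C(n,k) q^k (1 − q)^(n−k), summed over k = 0 to 4.

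| n | q | P(X ≥ 1) | P(X ≥ 5) |
|---|---|---|---|
| 10 | 1% | 9.6% | below 0.01% |
| 10 | 5% | 40.1% | 0.01% |
| 10 | 10% | 65.1% | 0.16% |
| 21 | 1% | 19.0% | below 0.01% |
| 21 | 5% | 65.9% | 0.32% |
| 21 | 10% | 89.1% | 5.2% |

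The row at n = 21 and q = 10% is extreme, since it makes every participant a transplant recipient. The last column covers false events alone, and true rejections would add to them. It also ignores the stopping rule's own wording and the committee review, both of which come before any halt. The P(X ≥ 1) column runs from about 10% to 89% as the assumptions change, so it shows only that the documents do not fix the size of the problem.

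**The case against.** **The plain reading may not be what happens.** Section 6.5 is framed around rejection itself: participants are asked about a diagnosis, and the search is for episodes. No coding procedure is written, and a sensible abstractor might apply the condition throughout. This stands in part. It rules out saying that such cases will be coded as rejection. It does not remove the point, because a case definition should not depend on the abstractor departing from its text.

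**A broad definition may be deliberate.** For safety surveillance, over-capture can be preferable to missed cases, and the definition cites a source that cannot be checked here. This also stands. It is a reason to keep treatment-only cases on view, but not to merge them with diagnosed rejection in one percentage.

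**The impact is limited.** The endpoint is secondary and descriptive, and with 21 enrolled each case can be described individually. Granted; this makes the point a clarification and no threat to the study.

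Three stronger readings are tempting and are not supported:
- *That false events could halt the study.* Section 13.26 requires rejection needing treatment without a known cause, followed by committee review, and five false events are improbable in most of the range above. A halt pauses enrolment and vaccination, and the synopsis says recruitment is over.
- *That conditions in Appendix 3 would generate false rejections.* The appendix lists diseases and says nothing about their treatment.
- *That the distortion is some number of percentage points.* What one case is worth follows from the denominator, which is not stated. The same arithmetic applies to any misclassification in a small study and says nothing about how often this one occurs.

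**Conclusion.** The gap in the definition is real and appears in both sections that state it. As written, a depleting agent or immune globulin given to a transplant recipient for a reason other than rejection meets the endpoint, and no other provision corrects this. The consequence is confined to the descriptive rejection count and percentage. Its size is unknown: it depends on how many of the 21 participants are transplant recipients and how often these agents were given for other reasons, and the documents state neither. The conclusion rests on the grammar of the sentence and on the absence of any narrowing text, not on an assumed frequency. It is a cheap improvement to how the outcome is classified and reported. It says nothing about how any patient should be treated.

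**What to change.** - In sections 6.5 and 10.4.2, apply the condition about another indication to every treatment-based alternative, so that steroid bolus and taper, depleting agent and immune globulin are handled alike.
- Record the charted indication for each such treatment, using the record search and medication history already planned.
- In the formal SAP that section 12.2 promises before database lock, report rejection with transplant recipients as the denominator. Show documented diagnoses and treatment-only cases separately, and list the treatment-only cases with their indication.

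The cost is one phrase in two sections, one abstraction field and one table split, with no added visit or sample. The downside is that a treated rejection with no charted indication could be missed from the main count. The separate treatment-only listing keeps it visible and preserves the sensitivity of the broad wording.

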7.0 STUDY DESIGN

7.1 Program Type / Scope of Study / Clinical Design / Sites

This will be a single-center, prospective, unblinded, non-randomized study of 141 immunosuppressed patients who are planning to receive a NVX-CoV2601 COVID-19 vaccine booster dose as standard of care and are willing to participate in the study. We have paused recruitment in 2023-2024 season due to low recruitment. We are extending the study to enroll an additional 120 immunosuppressed patients who are planning to receive a 2024/2025 COVID-19 vaccine booster dose as standard of care and are willing to participate in the study.

During the 2024/2025 season at least 35 patients will have inflammatory bowel disease and at least 35 patients will be a solid organ transplant recipient. After obtaining informed consent, individuals who meet the inclusion criteria and none of the exclusion criteria will be invited to participate in the study. Blood samples will be collected from each participant at the baseline visit (V1), at 1M post–booster (V2 visit), and 6M post–booster (V3).

Figure 1. Schematic of Visits:

7.2 Site Responsibilities Overview

The University of Wisconsin Hospital and Clinics will be the site of the study and will be responsible for coordinating activities, receiving and analyzing samples and data, and developing and updating the study protocol as needed. The UNC-developed data/web platform will be used to collect subject data and subject data will be stored on UNC platforms. A Data Transfer Use Agreement between UW and UNC will be executed before the sharing of data with UNC begins. UNC will obtain their own IRB approval.

Communication plan: Monthly conferences led by [name], PI, with research staff at UW. In this teleconference, the following will be discussed: recruitment, barriers to recruitment, and potential future protocol changes.

Adverse events/SAE/Unanticipated problems: All events, including adverse events to vaccines, IBD flares, transplant rejection, noncompliance, unanticipated events, protocol deviations, protocol violations, or serious adverse events will be reported to the regulatory bodies, including the IRB, as appropriate and per posted guidelines. The UW PI will be responsible for reporting any adverse events, as described in the Safety Reporting section.

Compliance with protocol: To ensure that no deviations from the protocol occur, the PI will review random cases every two months. Any deviations in the protocol will be investigated to evaluate the root cause for deviation. Noncompliance, unanticipated events, protocol deviations, protocol violations, or serious adverse events will be reported to the IRB per the posted guidelines.

7.3 Study Population Overview

Adults with established IBD on immunosuppression age 18-85 years and/or solid organ transplant recipients on systemic immunosuppressive therapy.

Inclusion criteria

- Have received at least three doses of a COVID-19 vaccine.
- On systemic immunosuppressive therapy for inflammatory bowel disease
 - o Immunomodulator (e.g. azathioprine, methotrexate)
 - Anti-TNF inhibitor
 - o II 12/23 blocker
 - o IL 23 blocker
 - Janus Kinase inhibitor
 - S1P inhibitor
- On systemic immunosuppressive therapy for solid organ transplant
 - Mycophenolate
 - o Tacrolimus or cyclosporine
 - Sirolimus or everolimus
 - Azathioprine
 - Corticosteroids
 - Belatacept

7.4 Study Duration

Major Study Periods

First Patient In (FPI) to Last Patient In (LPI):

6 months
LPI to Last Patient Out (LPO):

6 months
LPO to manuscript

4 months

We will publish the first manuscript based on the vaccine response baseline compared to 1 month post immunization 4 months after LPI.

The second manuscript will be published after completion of the study.

7.5 Ethical and Regulatory Considerations

Prior to initiating the study, IRB approval will be sought from the University of Wisconsin School of Medicine and Public Health.

Once approval is obtained, we will start recruitment. UW research staff (such as the PI and research coordinator) will hold monthly research conferences to ensure that there are no deviations in the protocol.

Compliance with protocol: To assure no deviations from protocol occur, random cases from the single-UW enrolling site will be reviewed by the PI to assure no deviations from protocol every 2 months. Any deviations in the protocol will be investigated to evaluate the root cause of the deviation.

The investigation will be conducted in compliance with the requirements for review by the IRB.

8.0 SELECTION AND WITHDRAL OF SUBJECTS

Patients with IBD (at least 35 subjects) and solid organ transplant recipients (at least 35 subjects)

8.1 Inclusion criteria

- Patient is between the ages of 18-85 years.
- Patient has a history of ulcerative colitis (UC), Crohn's disease, pouchitis, or indeterminate colitis diagnosed by standard clinical, radiographic, endoscopic, and histopathologic criteria.

And/or patient is a solid organ transplant recipient (e.g. lung, kidney, liver)

- Have received at least three doses of a COVID-19 vaccine.
 - Three mRNA vaccines

Or

- One or two viral vector vaccine and one or two mRNA vaccines.
- Female participant of non-childbearing potential (pre-menarche, current tubal ligation, hysterectomy, oophorectomy or post-menopause) and childbearing potential (if they had: practiced adequate contraception (include -IUD or equivalent, hormonal contraceptive (e.g. pill, patch, ring, implant or an injection used consistently and that has reached full effect prior to the first dose of vaccine), hysterectomy and/or a bilateral tubal ligation or bilateral oophorectomy) for 1 month prior to vaccination and agreement to use such for an additional 8 weeks after administration of the Novavax COVID-19 vaccine). Non-pregnant females with a negative pregnancy test who are willing to practice adequate contraception 8 weeks after administration of the Novavax COVID-19 vaccine.
- On one of the following treatment regimens
 - o IBD
 - Thiopurine Therapy Group: on azathioprine at least 2.0mg/kg or 6MP 1.0mg/kg
 - Anti-TNF Therapy Group: on maintenance therapy infliximab (at least every 8 weeks), golimumab (at least monthly), adalimumab (at least every 2 weeks), or certolizumab (at least monthly)
 - Anti-TNF Combination Therapy Group: on anti-TNF therapy as described above along with either 15mg of methotrexate or azathioprine at least 1.0mg/kg or 6MP 0.5mg/kg.
 - Vedolizumab Therapy Group: either vedolizumab monotherapy at least every 8 week dosing or combination therapy Group: on vedolizumab therapy at with azathioprine or methotrexate
 - Ustekinumab Therapy Group: either ustekinumab monotherapy or combination therapy with methotrexate or azathioprine.
 - Tofacitinib Therapy Group: on tofacitinib at least 5mg PO twice daily
 - Risankizumab Therapy: 360mg at least every 8 weeks
 - Mirikizumab: 200mg at least every 4 weeks
 - Upadacitinib Therapy Group: on upadacitinib at least 15mg PO daily
 - Ozanimod: at least 0.92mg once daily
 - Etrasimod: at least 2mg once daily

- Solid organ transplant recipient (on any dose of the following regimens: patients can be on more than one of the regimens below)
 - Mycophenolate
 - Tacrolimus or cyclosporine
 - Sirolimus or everolimus
 - Azathioprine
 - Corticosteroids
 - Belatacept

